An insufficient therapeutic effect may be determined prior to the planned duration of therapy in the study. This determination will require an assessment of clinical status including the synthesis of symptoms and signs data (both local and systemic). Subjects who are deemed to have an insufficient therapeutic effect should be discontinued from study drug therapy.

If a subject has daily blood cultures positive for *Candida* spp. through Day 7 despite appropriate study drug administration, this should be considered an insufficient therapeutic effect and study drug should be discontinued and salvage therapy initiated. The subject should remain in the study through the Follow-up visit (Days 52–59) to complete safety assessments and assess for mortality.

Seven days is the maximum number of daily positive blood cultures allowed prior to a change in antifungal therapy. The Investigator may determine that there is an insufficient therapeutic response prior to Day 7.

- Investigator discretion
 - Resistant Pathogen(s): In the event an organism resistant to ≥ 1 of the potential study drugs is isolated, the Investigator will determine whether the subject remains on study drug therapy. The Investigator may decide to continue study drug therapy if, in the Investigator's opinion, there is clear and continuing clinical improvement while on therapy.
 - The Investigator may decide to prematurely discontinue study drug therapy and to initiate an alternative and appropriate therapy if, in the Investigator's opinion, the subject is not benefiting from study drug.

NOTE: The Medical Monitor should be contacted to discuss whether to continue or prematurely discontinue a subject on the study drug in the event the subject requires systemic concomitant antifungal therapy.

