13.4.4 Additional Efficacy Analyses

The number and percentage of subjects with resolution of all systemic signs attributable at baseline to candidemia and/or invasive candidiasis at Day 5, Day 14 (± 1 day), Day 30 (-2 days) and Follow-up (Days 52–59) will be presented by treatment group in the mITT population.

The number and percentage of subjects who died up through the Follow-up visit (ACM) will be presented by treatment group in the mITT population. In addition, Kaplan-Meier (KM) methods will be utilized to analyze survival time in the mITT and ITT populations. Subjects who remain alive or are lost to follow-up will be censored at the last date known to be alive. Kaplan-Meier survival curves will be provided. The 25th, 75th percentiles and the median survival time as well as the probability of being alive at Day 5, Day 14, Day 30, and Day 55 will be determined by treatment group.

The time to the first negative blood culture (for those subjects enrolled with a positive blood culture) without subsequent positive culture from a sample drawn following the first dose of study drug will be summarized using KM methods. Subjects will be censored if they receive an alternative antifungal (i.e., other than study drug) for the treatment of the candidemia, died or were lost to follow up prior to having the negative blood culture. Kaplan-Meier survival curves will be provided. The 25th, 75th percentiles and the median survival time will be determined by treatment group.

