2.3.3. Time to First Negative Blood Culture

Time to first negative blood culture is defined in hours from the first dose of study drug to the first negative blood culture without subsequent positive cultures following the first pre-treatment blood culture confirmed positive for any *Candida* species. Blood culture results from both location 1 and location 2 need to be negative if the samples were taken from 2 locations on the same day. Subjects will be censored at the earliest start date and time of receipt of a new antifungal (i.e., other than study drug) for the treatment of candidemia received any time on/after the date and time of the first dose of study drug if it was used prior to having a negative blood culture. If a subject is lost to follow-up or died prior to having a negative blood culture, the subject will be censored at the date of the last blood culture. The details about the censoring rules under different scenarios are shown in the following table:

Blood Culture Result	Antifungal Use	Event (Negative Culture) or Censor	Event or Censoring Date
Negative blood culture without subsequent positive cultures	Not used or used after negative blood culture	Event	Earliest blood culture date with negative result
Negative blood culture obtained prior to first dose date and no subsequent positive cultures	Not used or used after negative blood culture	Censor	First dose date
No negative blood culture	Not used	Censor	Last blood culture date
No negative blood culture	Used	Censor	Earlier date between the last blood culture date and the antifungal start date

The number and percentage of subjects with a negative blood culture at 24 and 48 hours post first dose will also be provided by treatment group. The denominator will include subjects who were either not censored in the time to negative blood culture analysis or who were censored after 24 or 48 hours, respectively.

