4.3.4. Additional Efficacy Outcomes

Analyses for the additional efficacy endpoints will be performed using the mITT population.

Resolution of all systemic signs attributable at baseline to candidemia and/or invasive candidiasis for subjects receiving of Rezafungin for Injection and caspofungin at Day 5, Day 14 (± 1 day), Day 30 (-2 days) and Follow-up (Days 52-59) will be presented by treatment group. This analysis will be repeated for subjects additionally with mycological eradication.

All-cause mortality at Follow-up will be presented for the mITT population by treatment group using frequencies and percentage of subjects that were alive and deceased at Follow-up. In addition, Kaplan-Meier (KM) methods will be utilized to analyze survival time in the mITT and ITT populations. The probability of being alive at Day 5, Day 14, Day 30, and Day 55 will be determined by treatment group. In addition, the 25th, 50th (median), and 75th percentiles will be provided by treatment group. The number and percentage of subjects censored will be provided. KM survival curves will be provided. The number of subjects at risk and number died in each treatment group will be displayed below the x-axis at day= 0, 5, 14, 30, 55. Survival status will be provided in a by-subject listing.

The time to the first negative blood culture without subsequent positive culture from a sample drawn following the first dose of study drug will be summarized using KM methods for mITT population. The calculation will be in reference to the first dose date. For subjects who have negative blood culture prior to the first dose of study drug without subsequent positive culture, the time to the first negative blood culture will be set to zero. A log-rank test will be performed to test for differences in survival curves between treatment groups. Subjects will be censored if they receive an alternative antifungal (i.e., other than study drug) for the treatment of the candidemia, died or were lost to follow up prior to having the negative blood culture (see Section 2.3.3). KM survival curves will be provided. The 25th, 75th percentiles and the median survival time and 95% CIs will be determined by treatment group. This analysis will be repeated for the following subsets among the subjects with any post-baseline blood cultures: 1) Subjects with

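### In the exploratory time-to-first-negative-blood-culture analysis, censoring uncleared deaths and rescues overstates clearance on study drug, and early ones leave the 24/48-hour denominators

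*SAP*

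**What the plan says.** The endpoint is listed under SAP 2.3, Exploratory Efficacy Outcomes. "Time to first negative blood culture is defined in hours from the first dose of study drug to the first negative blood culture" with no later positive.

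Failures before that point are censored:

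- **Rescue.** "Subjects will be censored at the earliest start date and time of receipt of a new antifungal" for candidemia. For a subject with no negative culture who received rescue, the accompanying table uses a date that can be earlier: "Earlier date between the last blood culture date and the antifungal start date".
- **Death.** If a subject "died prior to having a negative blood culture, the subject will be censored at the date of the last blood culture". Protocol 6.1.7 allows cultures every other day, so this date can precede the death.
- **24 and 48 hours.** For these percentages the rule reads: "denominator will include subjects who were either not censored in the time to negative blood culture analysis or who were censored after 24". The same applies at the 48-hour cut.

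Protocol 13.4.4 has the same rule: "Subjects will be censored if they receive an alternative antifungal (i.e., other than study drug) for the treatment of the candidemia, died". Loss to follow-up before clearing is treated alike. SAP 4.3.4 adds the comparison, "A log-rank test will be performed to test for differences in survival curves between treatment groups", and repeats the analysis in four subsets. Neither document plans a competing-risk analysis or a 24/48-hour rate that keeps uncleared deaths and rescues in the denominator.

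**The concern.** Censoring at rescue is not neutral here. Under Protocol 7.4.2, when daily cultures stay positive through Day 7, "this should be considered an insufficient therapeutic effect and study drug should be discontinued and salvage therapy initiated"; the investigator may reach that judgement sooner. Subjects rescued on this ground leave the risk set because they have not cleared, whereas Kaplan-Meier assumes they would have cleared like those who remain. Death is different in kind, because clearance cannot follow it. In both cases, one minus Kaplan-Meier reads higher than the proportion who actually clear on study drug.

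The 24/48-hour percentages have a separate problem. A subject who dies or is rescued while positive before the cut is removed from the denominator, so the reported rate rises with each such failure. SAP Table 2-3 counts the same two events as mycological failure. One subject can therefore be a failure in that table and missing from the 48-hour rate.

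At stake is how the speed-of-clearance display is read. If one arm has more early failures, its deficit can be hidden or reversed.

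**Working it through.** **Inputs.** The documents give no clearance rate, failure rate or event count for this endpoint, so every rate below is an assumption. The one planning figure used is 92 mITT subjects per arm (Protocol 13.8). It reproduces: 2 × 0.21 × (1.960 + 0.842)² / 0.2² = 82.4, and with continuity correction 82.4/4 × [1 + √(1 + 4/(82.4 × 0.2))]² = 92.1.

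**Step 1: constant hazards.** Let λ be the daily hazard of clearance and g the daily hazard of death or rescue while uncleared. Take λ = ln 2 / 2 = 0.347 in both arms (median 2 days).

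- Cleared on study drug by t: C(t) = λ/(λ+g) × [1 − exp(−(λ+g)t)]
- Failed uncleared by t: F(t) = g/(λ+g) × [1 − exp(−(λ+g)t)]
- One minus Kaplan-Meier: 1 − exp(−λt)
- SAP rate at the cut: C(t) / [1 − F(t)]

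| g per day | F, 48 h | C, 48 h | SAP rate, 48 h | C, Day 7 | 1 − KM, Day 7 |
|---|---|---|---|---|---|
| 0.02 | 2.8% | 49.1% | 50.6% | 87.3% | 91.2% |
| 0.05 | 6.9% | 47.9% | 51.4% | 81.9% | 91.2% |
| 0.10 | 13.2% | 45.8% | 52.8% | 74.2% | 91.2% |

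For g = 0.10 at 48 h: 0.458 / (1 − 0.132) = 0.528. True clearance falls down the column while the SAP rate rises.

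**Step 2: counts at 48 hours.** This needs no hazard model. The SAP rate is cleared / (N − censored by the cut).

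- 51/92 cleared with 2 early failures, against 48/92 with 9: all-subject rates 55.4% vs 52.2%; SAP rates 51/90 = 56.7% vs 48/83 = 57.8%.
- 51/92 cleared in both arms with 0 vs 5 early failures: 55.4% in both; SAP rates 51/92 = 55.4% vs 51/87 = 58.6%.
- Only blood-culture-positive subjects enter, so N will be smaller. With 65 per arm, 36 vs 34 cleared and 1 vs 6 early failures: 55.4% vs 52.3% becomes 36/64 = 56.2% vs 34/59 = 57.6%.

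**Step 3: failures concentrated in slow clearers.** Assume 30% slow clearers in both arms, clearance hazards 0.8 (fast) and 0.08 (slow) per day, failure hazard 0.01 in fast clearers, and 0.03 (arm A) vs 0.25 (arm B) in slow clearers. With no failures at all, Day 7 clearance would be 1 − [0.7 × exp(−5.6) + 0.3 × exp(−0.56)] = 82.6% in both arms. Simulation gives Kaplan-Meier 83.1% in A and 89.5% in B, against cumulative incidence of 80.6% and 75.4%. In 2,000 simulated trials of 92 per arm, the planned log-rank statistic favoured B in 78%. With failures held as not cleared to Day 14, it favoured B in 19%.

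**Step 4: who is affected by which rule.** A subject switched around Day 7, with cultures continuing past 48 hours, is censored after both cuts and stays in both denominators as not negative. That switch affects only the Kaplan-Meier curve and log-rank test. The 24/48-hour rates lose only subjects censored at or before the cut, but because censoring can be dated to the last culture, a somewhat later death or switch can also drop out.

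**The case against.** The strongest reply has four parts.

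- **Status and safeguards.** The endpoint is exploratory. Mycological response at Day 5 and Day 14 is a secondary outcome, counts death and change of antifungal as failure, and uses the whole analysis population (SAP 2.2 and 2.2.2). An arm with many early failures would show a deficit there, in mortality and in global cure. This stands, and it limits the consequence. It does not correct the 24/48-hour rates or the curves.
- **The log-rank test.** A log-rank test with competing events censored is a recognised comparison of cause-specific hazards. In Step 1 the clearance hazards are equal, and the planned test would correctly find no difference. A reader might infer that the test is invalid and should give way to Gray's test. The documents do not support that: Gray's test would mix death and rescue into a question about speed. What remains is that the hazard comparison is distorted when removal depends on not clearing, as in Step 3, and that the curves will be read as clearance probabilities.
- **The denominator rule has a legitimate use.** Subjects already negative before first dose are censored at first dose and so excluded. Subjects with no later culture before the cut, and no death or switch, have unknown status. A reader might count these last as known not to have cleared, but they are not.
- **Assumed rates.** A hazard of 0.10 per day is high. The only documented rate, 20% mortality by Day 30, is −ln(0.8)/30 = 0.007 per day if constant; rescue rates are not given. At 0.05 per day the reversal is under one point (51.4% vs 50.6%). This stands for size. The direction of the 24/48-hour effect is algebraic.

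**Conclusion.** The point holds for this exploratory analysis. One minus Kaplan-Meier overstates clearance on study drug whenever subjects die or are rescued uncleared, and Protocol 7.4.2 makes the rescue part informative. The 24/48-hour rates rise with each uncleared death or rescue censored by the cut, and so can narrow or reverse a difference between arms.

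In the illustration at 48 hours, a true deficit of 3.3 points (49.1% vs 45.8%) becomes an apparent advantage of 2.2 points (50.6% vs 52.8%) at 0.02 vs 0.10 per day. A deficit of 1.2 points becomes an advantage of 0.8 at 0.02 vs 0.05. These figures rest on assumed constant hazards and equal clearance hazards in the two arms. With similar early failure rates, the comparison between arms would move little, although both levels would still be overstated.

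Two stronger readings should be set aside. A reader might infer that Day 7 rescues drive the 24/48-hour bias; those subjects generally remain in the denominators. A reader might also infer that the trial's main results are compromised; mortality, global cure and mycological response count death as an event or failure, so the primary and secondary conclusions are unaffected.

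**What to change.** In SAP 2.3.3, keep in the 24/48-hour denominators, as not cleared, every subject who died or started a new antifungal for candidemia by the cut without a negative culture. Continue to exclude subjects already negative before first dose, and those whose status is unknown without death or switch. State one rule for subjects whose last culture precedes the cut but who die or switch after it, and align the text and table on the rescue censoring date.

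In SAP 4.3.4, retain the Kaplan-Meier curves and log-rank test. Beside them, report cumulative incidence of clearance by arm, with death and new antifungal for candidemia as competing events.

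The cost is minor SAP wording and programming on data already collected. Reported clearance rates will be somewhat lower.

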2.3.4. Clinical Outcomes by Baseline *Candida* species

The number and percentage of subjects who died by Day 30 (-2), were a global cure (as confirmed by the DRC) at Day 14 (± 1), were a mycological eradication at Day 14 (± 1 days),

were a radiological response (for subjects with invasive candidiasis documented by radiologic/imaging evidence) at Day 14 (± 1 days) and were a clinical cure at Day 14 (± 1 day) will be summarized by baseline *Candida* spp. and treatment group for subjects in the mITT population.

Mortality (Day 30 [-2]), global cure, mycological eradication, radiologic cure (for subjects with invasive candidiasis documented by radiologic/imaging evidence) and clinical cure by baseline *Candida* spp. and minimal inhibitory concentration (MIC) distribution for Rezafungin for Injection, caspofungin and fluconazole at Day 14 (-2) will be summarized by treatment group for subjects in the mITT population.

2.4. Health Outcome Measures

For subjects admitted to the Intensive Care Unit (ICU) on or after Study Day 1, the number of ICU admissions, the time to discharge for each admission and the total length of stay in the ICU across all admissions will be summarized by treatment group. The number and percentage of subjects re-admitted after discharge by Day 30 (-2 days) and by Follow-up (Days 52-59) will be presented by treatment group in the mITT population for all re-admissions, for re-admissions related to infectious disease and again for re-admissions related to Candidiasis.

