13.6 Health Economics Outcome Research

Descriptive statistics of the total length of hospital stay and the total length of ICU stay will be provided by treatment group.

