4.4. Analysis of Health Outcomes

The number and percentage of subjects admitted to the Intensive Care Unit (ICU) on or after Study Day 1 will be summarized by treatment group in the mITT population. For those subjects who did not die before hospital/ICU discharge, the time to discharge for each admission to hospital and to ICU will be generated and the longest length of stay for each subject will be summarized using descriptive statistics by treatment group in the mITT population. For subjects admitted to the hospital and to the ICU, the number of hospital/ICU admissions will be determined and the number and the percentage of the subjects with no ICU admission, 1 ICU admission, and 2 ICU admissions will be presented. In addition, for those subjects who did not die before hospital/ICU discharge, the total number of days in hospital, in ICU, and in general ward across all admissions will be determined. The total number of days in hospital is defined as the total number of days in hospital during the study period (i.e., if admission date is earlier than the first dose date, the number of days is defined as discharge date – first dose date +1; if admission date is on or later than first dose date, the number of days is defined as discharge date – admission date +1). The number of days from the initial admission and the one from re-admission (if applicable) will be summed to get the total number of days. For the subjects with missing hospital discharge date, the end of study date or the ICU discharge date, whichever is later, will be used for the discharge date. Descriptive statistics will be used to summarize the total number of days in hospital, in general ward, and for those admitted to the ICU, the total number of days in ICU, by treatment group in the mITT population. Similarly, the total number of days in hospital, in ICU, and in general ward at time of enrollment (defined as randomization date – admission date +1) will be summarized.

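### SAP 2.4 limits the ICU measures to subjects admitted to the ICU on or after Study Day 1, and SAP 4.4 does not clearly bring back those already in the ICU at first dose

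*SAP*

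**What the plan says.** SAP 2.4 (Health Outcome Measures) sets the group first: "For subjects admitted to the Intensive Care Unit (ICU) on or after Study Day 1, the number of ICU admissions". The same sentence goes on to time to discharge for each admission and total ICU length of stay. Study Day 1 is the day of first study drug administration (SAP 2.1).

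SAP 4.4 (Analysis of Health Outcomes) has several relevant parts:

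- **ICU count (mITT subjects).** "The number and percentage of subjects admitted to the Intensive Care Unit (ICU) on or after Study Day 1 will be summarized by treatment group".
- **Total stay.** Among subjects who did not die before discharge, "the total number of days in hospital, in ICU, and in general ward across all admissions will be determined".
- **Stays that began before treatment.** In defining total days in hospital: "if admission date is earlier than the first dose date, the number of days is defined as discharge date" minus first dose date plus 1.
- **Who enters the ICU-days table.** "for those admitted to the ICU, the total number of days in ICU, by treatment group in the mITT population".
- **Stay accrued by enrollment.** A separate summary of "the total number of days in hospital, in ICU, and in general ward at time of enrollment", calculated as randomization date minus admission date plus 1.

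Protocol 13.6 says: "Descriptive statistics of the total length of hospital stay and the total length of ICU stay will be provided by treatment group". Protocol 10.3 lists both lengths of stay as exploratory outcomes. Neither section restricts by admission date. SAP 6 states that the SAP makes no changes to the analyses defined in the protocol.

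**The concern.** Some subjects will probably be in the ICU when treatment starts. The protocol records ICU admission and discharge at Screening and stratifies randomization partly on an APACHE II score of 20 or more. The at-enrollment summary in SAP 4.4 shows that the authors expected such subjects.

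Under the literal rule in SAP 2.4, a subject in the ICU from before Day 1 to Day 20 has no ICU measure, while a ward patient moved to the ICU on Day 10 for two days has all three. The ICU-stay table would then describe only part of the ICU use that the protocol planned to report. Its membership would also depend largely on events after treatment starts, which treatment could influence, so the two arms' tables need not compare like with like.

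**Working it through.** The documents give no sample size, power or other figure for ICU outcomes, so there is nothing to reproduce. The check is a comparison of the sections, followed by two small illustrations.

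**Step 1: where the date limit applies.**

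- SAP 2.4: it governs ICU admissions, time to discharge and total ICU stay.
- SAP 4.4, opening sentence: it governs the number and percentage admitted to the ICU.
- SAP 4.4, length-of-stay sentences: it is not restated.
- Protocol 10.3 and 13.6: there is no limit.

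SAP 2.4 therefore conflicts with the protocol, and SAP 4.4 is internally mixed.

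**Step 2: whether SAP 4.4 settles it.** The count-from-first-dose rule defines days in hospital. No matching sentence covers days in the ICU. The ICU-days table is for those admitted to the ICU, which can mean any ICU admission or the group in the opening sentence. The at-enrollment summary covers days up to randomization, so it cannot supply on-study ICU days.

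**Step 3: one subject under the possible readings.** Take ICU admission 5 days before first dose and discharge on Study Day 10. Index the first dose date as 0, so admission is −5 and discharge is 9.

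- Literal SAP 2.4 rule, with no later ICU admission: not in the table.
- Hospital-day rule extended to ICU days: 9 − 0 + 1 = 10 days.
- Stay counted in full: 9 − (−5) + 1 = 15 days.
- At-enrollment summary, if randomized on the day of first dose: 0 − (−5) + 1 = 6 days.

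The same record gives no entry, 10 days or 15 days in the ICU-stay table, depending on the programmer's reading.

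**Step 4: how many subjects this could touch.** The planned mITT size is 184 (Protocol 13.8). The share whose ICU stay began before Day 1 is not given, so it is assumed:

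- 10%: 0.10 × 184 = 18.4, about 18 subjects.
- 30%: 0.30 × 184 = 55.2, about 55.
- 50%: 0.50 × 184 = 92.

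These counts assume that none of these subjects has a further ICU admission. SAP 2.4 selects subjects, so one who left the ICU and was admitted again after Day 1 would qualify.

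**Step 5: deaths.** The stay summaries in SAP 4.4 also begin from a survivor group: "For those subjects who did not die before hospital/ICU discharge". This is a second selection after randomization, and it is stated without ambiguity.

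**The case against.** The best defense is that SAP 4.4 is the detailed analysis section and should prevail over the short definition in SAP 2.4. Its length-of-stay sentences carry no date limit, it totals days over all admissions, and it reports ICU days already accrued at enrollment. SAP Appendix 9 records that health-outcome derivation rules were added in V3.0 and the at-enrollment summary in V4.0, which suggests that SAP 4.4 is the more considered text. This stands in part: the documents do not establish that subjects already in the ICU will be left out of the stay tables. It does not remove the conflict, because SAP 2.4 remains in force and the first-dose rule is not extended to ICU days.

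A reader might go further and infer any of the following. The documents do not support them.

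- **That the comparison covers only subjects who deteriorated after randomization.** An ICU admission on Day 1 qualifies. Because Protocol 9.2.1 places randomization on Day 1 immediately before dosing, that admission may precede randomization. Nor must an ICU admission mean deterioration; it could follow a source-control procedure.
- **That the rule captures only 17% to 33% of ICU users.** This comes from 10/60 and 10/30, assuming 20% to 50% already in the ICU and 10% admitted later. None of these shares is in the documents, and the result presupposes the disputed reading.
- **That ICU days must be averaged over all mITT subjects with zeros for non-users.** SAP 4.4 already tabulates subjects with no ICU admission. Days among users shown beside that proportion is an acceptable presentation.

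**Conclusion.** The inconsistency is real and minor. SAP 2.4, and the opening of SAP 4.4 for the ICU count, apply an admission-date limit that the protocol does not have, and SAP 4.4 does not clearly restore subjects already in the ICU at first dose. The statement in SAP 6 is inaccurate if SAP 2.4 is followed as written.

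The size cannot be fixed from the documents. The figures of about 18, 55 or 92 of 184 rest on assumed shares of 10%, 30% or 50%, the literal SAP 2.4 rule, and no later ICU admission. Length of ICU stay carries no hypothesis, margin or alpha, so no primary, secondary or safety conclusion depends on it.

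**What to change.** Make the same change in SAP 2.4 and 4.4:

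- Define ICU use as any day in the ICU on or after Study Day 1, whatever the admission date.
- For ICU stays that began before first dose, count days as ICU discharge date minus first dose date plus 1, matching the hospital-day rule.
- Report new ICU admissions after first dose separately from stays already under way at first dose.
- Beside each stay summary, give the number and percentage of subjects per arm who died before discharge, since the summaries exclude them.

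If the sponsor prefers to keep the admission-date limit, SAP 6 should list it as a change from the protocol.

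The cost is a few sentences in the SAP and the matching table shells. The existing SAP derivations already call for ICU admission and discharge dates, so no new data collection is needed.
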